1.1 Rationale

Immunocore is developing a new biological entity, IMCnyeso, for the treatment of multiple indications where tumors are positive for the cancer-testis antigens New York esophageal squamous cell carcinoma-1 (NY-ESO-1) and/or L antigen family member-1 isoform A (LAGE-1A). The effector function of IMCnyeso (anti-CD3) works by binding and activating T cells via cluster of differentiation 3 (CD3). The effector T cells that bind to IMCnyeso and the tumor can be tumor-specific cells (tumor-infiltrating lymphocytes [TIL]) but circulating polyclonal T cells may also be activated as they traffic through the tumor through normal blood supply. IMCnyeso-mediated activation of these T cells stimulates the immune system to attack the target tissue.

IMCnyeso was evaluated in a series of in vitro investigations to assess potential anti-tumor activity in patients with tumors that express NY-ESO-1 and/or LAGE-1A. These data can be summarized as follows:

- In vitro, IMCnyeso potently recruits and activates healthy donor and cancer patient peripheral blood mononuclear cells (PBMCs), leading to the release of pro-inflammatory cytokines, chemokines, and killing of cancer cell targets. The fullest extent of redirected T cell killing can take up to 72 hours.

- In vitro, IMCnyeso potently recruits and activates CD3 positive T cells including CD8 positive and CD4 positive T cells resulting in cancer-cell killing, polyfunctional T cell activation, proliferation, and expansion of T cells.

These data demonstrate that IMCnyeso is a potent tumor-killing agent. Therefore, an investigation into the effects of the drug in patients with tumors expressing NY-ESO-1 and/or LAGE-1A is warranted.

For additional clinical information regarding IMCnyeso, refer to the latest version of the Investigator's Brochure.

2 Objectives

2.1 Primary Objectives

The primary objective in Phase I is to identify the MTD and/or the RP2D of IMCnyeso, as a monotherapy, when administered weekly to patients with advanced NSCLC, melanoma, urothelial cancer, and synovial sarcoma. The primary objective in Phase II is to assess the preliminary anti-tumor activity of IMCnyeso as monotherapy in advanced NSCLC, urothelial cancer, and synovial sarcoma.

2.2 Secondary Objectives

The following secondary objectives apply to both Phases I and II (reported separately) unless otherwise noted:

- To characterize the safety and tolerability of IMCnyeso (Phase II only)
- To assess the preliminary anti-tumor activity of IMCnyeso as monotherapy
- To characterize the PK profile of IMCnyeso as monotherapy
- To evaluate the preliminary incidence of anti-IMCnyeso antibody formation following multiple infusions of IMCnyeso

2.3 Exploratory Objectives

[REDACTED]

- [REDACTED]
- [REDACTED]
- [REDACTED]

[REDACTED]

3 Investigational Plan

3.1 Overall Study Design and Plan

[figure not shown]
IMCnyeso-101 is a Phase I/II, multi-center, open-label, first in human (FIH), multi-ascending dose study of monotherapy IMCnyeso in HLA-A*0201 positive patients with advanced NY-ESO-1 and/or LAGE-1A positive solid tumors.

The study will be conducted in 2 phases:

- Phase I – dose escalation in 4 diseases (advanced NSCLC, melanoma, urothelial carcinoma, and synovial sarcoma) to determine the MTD and/or RP2D of IMCnyeso as a monotherapy. The decisions regarding dose escalation of IMCnyeso will be made by the Study Safety Team (SST), which will consist of the Study Investigators, the Sponsor Medical Monitor, and a Statistician. Dosing decisions will be made following a review of all relevant data available, from all dose levels evaluated in the ongoing study, including safety information, DLTs, all \geq Grade 2 toxicity data, PK, and pharmacodynamic data from evaluable patients in the dose-determining set (DDS) (see Section 4.3.6). The SST will be guided by the recommendation from the Bayesian Logistic Regression Model (BLRM) (see reference 1) since the Phase I design uses N-Continual Reassessment Method (N-CRM) of dose escalation with overdose control (EWOC) (see Section 15.2).
- Phase II – following the identification of the MTD and/or RP2D in Phase I, patients may be enrolled into the 3 Phase II expansion cohorts (NSCLC, urothelial carcinoma, and synovial sarcoma) to make a preliminary assessment of the anti-tumor activity of IMCnyeso as a single agent in these disease settings. Initially, up to 9 patients may be enrolled in each Phase II cohort. If there is at least one response, at the discretion of the sponsor up to an additional 15 patients may be accrued for a total of up to 24 patients.

The design is summarized in **Figure 1** below:

Figure 1 - IMCnyeso-101 Study Design

HLA = human leukocyte antigen; NSCLC = non-small cell lung cancer; RP2D = recommended Phase II dose.

The number of patients in the Phase I escalation part of the study is estimated to be 27 patients. There is no upper limit to the sample size in Phase I. However, in 80% of the simulations conducted, the sample size was < 33 patients (see Section 4.1).

3.2 Study Endpoints

3.2.1 Primary Endpoint

The primary endpoints in Phase I are:

- The incidence of dose limiting toxicities

- The incidence and severity of AE and SAE
- The changes in laboratory parameters, vital signs, and ECGs
- The dose interruptions, reductions, and discontinuations

The primary endpoint in Phase II is the best overall response (BOR) as determined by RECIST v1.1.

3.2.2 Secondary Endpoints

For both phases, the following will be analyzed:

- Progression-free Survival (PFS)
- Duration of Response (DoR) by RECIST v1.1
- Overall Survival (OS)
- Serum PK parameters (e.g. AUC, Cmax, Tmax, $t_{1/2}$) after single and multiple doses
- The incidence of anti-IMCnyeso antibody formation

For Phase I only, the following secondary endpoint will also be analyzed:

- Best Overall Response (BOR)

For Phase II only, the following secondary endpoints will also be analyzed:

- Incidence and severity of AE and SAE
- Changes in laboratory parameters, vital signs, and ECGs
- Dose interruptions, reductions, and discontinuations

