4 STUDY OBJECTIVES AND ENDPOINTS

Study objectives and corresponding endpoints are shown in [Table 4-1](#).

Table 4-1: Study Objectives and Endpoints

Objectives	Endpoints
Primary - Phase I	
To identify the MTD and/or the RP2D of IMCnyeso, as a monotherapy, when administered weekly to patients with advanced NSCLC, melanoma, urothelial cancer, and synovial sarcoma	Incidence of dose-limiting toxicities Incidence and severity of AE and SAE Changes in laboratory parameters, vital signs, and ECGs Dose interruptions, reductions, and discontinuations
Primary – Phase II	
To assess the preliminary anti-tumor activity of IMCnyeso as monotherapy in advanced NSCLC, urothelial cancer, and synovial sarcoma	BOR as determined by RECIST v1.1
Secondary- Phase II	
To characterize the safety and tolerability of IMCnyeso	Incidence and severity of AE and SAE Changes in laboratory parameters, vital signs, and ECGs Dose interruptions, reductions, and discontinuations
Secondary- Phase I and Phase II	
To assess the preliminary anti-tumor activity of IMCnyeso as monotherapy	Phase I: BOR, PFS, and DoR by RECIST v1.1; OS Phase II: PFS, and DoR by RECIST v1.1; OS
To characterize the PK profile of IMCnyeso as monotherapy	Serum PK parameters (eg, AUC, C _{max} , T _{max} , t _{1/2}) after single and multiple doses
To evaluate the preliminary incidence of anti-IMCnyeso antibody formation following multiple infusions of IMCnyeso	Incidence of anti- IMCnyeso antibody formation and its impact on PK
Exploratory	
[REDACTED]	[REDACTED]

Objectives	Endpoints
[REDACTED]	[REDACTED] [REDACTED] [REDACTED]
[REDACTED]	[REDACTED] [REDACTED] [REDACTED]

AE = adverse event; AUC = area under the curve; BOR = best overall response; CD# = cluster of differentiation #; C_{max} = maximum observed concentration; [REDACTED]; [REDACTED]; DoR = duration of response; ECG = electrocardiogram; [REDACTED]; [REDACTED]; MTD = maximum tolerated dose; NSCLC = non-small cell lung cancer; [REDACTED]; PFS = progression-free survival; PK = pharmacokinetic; RECIST = Response Evaluation Criteria in Solid Tumors; [REDACTED]; RP2D = recommended Phase II dose; SAE = serious adverse event; t_{1/2} = terminal elimination half-life; [REDACTED]; T_{max} = time of maximum concentration; [REDACTED].

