9.6.3 Pharmacokinetics and Immunogenicity

The PK parameters that will be assessed are presented in [Table 9-1](#).

Table 9-1: Pharmacokinetic Parameters to be Analyzed

Parameter	Definition
AUC _{last}	The area under the curve (AUC) from time 0 to the last measurable concentration sampling time (t _{last}) (mass × time × volume ⁻¹)
AUC _{inf}	The AUC from time 0 to infinity (mass × time × volume ⁻¹)
C _{max}	The maximum (peak) observed plasma, blood, serum, or other body fluid drug concentration after single-dose administration (mass × volume ⁻¹)
T _{max}	The time to reach maximum (peak) plasma, blood, serum, or other body fluid drug concentration after single-dose administration (time)
t _{1/2}	The elimination half-life associated with the terminal slope (λz) of a semi logarithmic concentration-time curve (time). Use qualifier for other half-lives
CL	The total body clearance of drug from the plasma (volume × time ⁻¹)
V _Z	The apparent volume of distribution during terminal phase (associated with λz) (volume)
AR	Accumulation ratio = maximum observed concentration (C _{max} [multiple dose]/C _{max} [single dose])

The safety analysis set will be used in all PK data analysis and PK summary statistics.

Descriptive statistics of all PK parameters for IMCnyeso will include arithmetic and geometric mean, median, standard deviation and coefficient of variation, geometric coefficient of variation and minimum and maximum. Zero concentrations will not be included in the geometric mean calculation. Since T_{max} is generally evaluated by a non-parametric method, median values and ranges will be given for this parameter. Missing concentration values will be reported as is in data listings. Concentration values below lower limit of quantitation will be handled as 0 in summary statistics and reported as is in data listings. Any missing PK parameter data will not be imputed.

The PK data will be displayed graphically. Displays will include individual patient plasma concentration profiles (on the linear and log-scale) versus time and geometric mean plasma concentration (\pm standard deviation) versus time, stratified by dose.

Scatter plots of PK parameters versus dose, or log-dose will also be considered to assess dose proportionality. In a preliminary assessment of dose proportionality, log-transformed AUC and C_{max} parameter estimates will be examined using the Power Model:

$$\text{parameter} = e^a (\text{dose})^b$$

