Section 4	Redundant body text was removed; objectives and corresponding endpoints are shown in table format only	Removed redundant information and improve organization
Section 2.1, Section 3.1, Section 4	The primary objective for Phase II was changed from “to further explore the safety and tolerability of the identified RP2D” to preliminary efficacy (BOR per RECIST v.1.1). Safety and tolerability is a secondary objective for Phase II.	To align with the goals of the Phase II portion of the study
Section 4	A secondary efficacy objective (based on RECIST v1.1) was added for Phase I	Efficacy is evaluated in Phase I but previously was not associated with a study objective
Section 4, Section 7	Response will no longer be evaluated per modified irRECIST	To simplify study conduct and align with current standards in the field
Section 4	The secondary PK endpoint was clarified to indicate that serum PK parameters would be determined after single and multiple doses	To clarify scope of planned analysis
Section 4	The secondary ADA endpoint was updated to include the impact of ADA on PK	To clarify scope of planned analysis
Section 4	[REDACTED]	[REDACTED]

Section in Amendment 1	Change	Rationale
Section 4	[REDACTED]	[REDACTED]
Section 4	[REDACTED]	[REDACTED]
Section 5.1	Shortened description of patient population	To remove redundant information
Section 5.2, Section 5.3	Organized eligibility criteria by topic and simplified	To aid in protocol compliance
Section 5.2	Clarified prior treatment requirements for Phase I to “Patients must be relapsed from, refractory to, or intolerant to all approved and available classes of therapy known to provide clinical benefit for their condition”	To clarify study inclusion criteria
Section 5.2	Clarified prior treatment requirements for Phase II to note that required therapies may have been given in the adjuvant setting if disease progression occurred during or within 6 months of completing adjuvant therapy, and patients with NSCLC with a genomic tumor aberration (eg, EGFR, ALK) that is targeted by Health Authority-approved agent(s) must be relapsed from, refractory to, or intolerant of relevant targeted agent(s).	To align with standard of care

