Pharmacokinetic parameters will be calculated by non-compartmental methods utilizing Phoenix WinNonlin (Certa version 8.2 or higher, Princeton, NJ, US) utilizing the linear/log trapezoidal methods. For parameter calculations, concentration values reported as LLOQ at pre-dose will be treated as zero (0), all other timepoints reported as LLOQ will be treated as missing. The following PK parameters will be calculated for individual patients where possible:

Cycle 1 Day 1

- T_{max} – time to maximum concentration observed
- C_{max} – maximum concentration observed
- AUC_{last} – area under the concentration time profile from pre-dose to last measurable concentration

Cycle 1 Day 8

- T_{max} – time to maximum concentration observed
- C_{max} – maximum concentration observed
- AUC_{tau} – area under the concentration time profile over the dosing interval

Cycle 1 Day 15

- T_{max} – time to maximum concentration observed
- C_{max} – maximum concentration observed
- AUC_{tau} – area under the concentration time profile over the dosing interval

Additional PK parameters may be calculated as the analysts determines meaningful at the time of the analysis (e.g. clearance [CL], terminal elimination half-life [t_{1/2}], steady state volume of distribution [V_{ss}], etc.)

The following summaries/analyses will be provided for PK parameters:

- Listings of pharmacokinetic parameters by cohort and dose (Cycle and Day).
- Summary of descriptive statistics of IMCnyeso PK parameters by cohort and dose

- The statistics to be presented include the n, arithmetic and geometric mean, median, standard deviation (Std), coefficient of variation (%CV), minimum, and maximum.

Any missing PK parameter data will not be imputed.

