10.2 Immunogenicity

Anti-drug Antibody (ADA) analysis will be used to evaluate immunogenicity responses. The frequency of ADA at baseline and following treatment will be summarized. All analyses will be reported in the CSR and/or a stand-alone report.

Sample ADA values at each visit and time-point will be collected in the following formats, from a third-party vendor:

- Binding ADA result
 - Positive: Final result in sample results spreadsheet (SRS) is Positive
 - Negative: Final result in SRS is Negative and PK value is < drug tolerance limit of assay (200 ng/mL, which is equivalent to 200,000 pg/mL)
 - Inconclusive: Final result in SRS is Negative and PK value is \geq drug tolerance limit of assay (200 ng/mL, which is equivalent to 200,000 pg/mL) or unknown
 - Unevaluable: Sample was unable to be analyzed (insufficient volume, wrong matrix, etc.)
- Binding ADA Titer value

Missing ADA values will be reported as is in data listings, as ‘No Result’ or ‘No Sample’.

For each patient, the final ADA status (derived from the cumulative ADA sample results for that patient) will be summarized. This will include:

- ADA status (Unevaluable, Positive, Negative)
- ADA Characterization (Treatment-induced, Treatment-boosted, or Pre-existing ADA)
- Time to ADA Onset for treatment-induced ADA patients
- ADA Duration category (Transient ADA response or Persistent ADA response)
- Max titer for treatment-induced ADA patients
- Peak fold increase in titer for treatment-boosted ADA patients

At a study level, the ADA data summaries will include:

- The number (%) of patients who are ADA-positive at baseline – see ADA *prevalence* at Baseline definition below.
- The number (%) of evaluable patients – see ADA Evaluable Subset definition below.
- The number (%) of patients who are ADA-positive at follow-up – see Overall ADA *incidence* definition below.
- The number (%) of patients who are ADA-negative at follow-up - see ADA Negative Subjects definition below.
- The number (%) patients with a treatment-induced ADA (from baseline negative) – see Treatment-induced ADA *incidence* definition below.

- The number (%) patients with a treatment-boosted (≥ 4 -fold) (from baseline positive) - see Treatment-boosted (≥ 4 -fold) ADA *incidence* definition below.
- The max titer from patients with treatment-induced ADA. Descriptive statistics including the median, IQR of the max titer will also be shown.

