10.3 Pharmacodynamics

Cytokines and lymphocytes are analyzed and are covered by this SAP. No other pharmacodynamics analysis would be performed.

11 Interim Analysis

No formal interim analysis is planned during Phase I. The BLRM will be updated after each dose-escalation cohort and the MTD / RP2D will be determined at the end of Phase I (see Section 3.1).

A formal interim analysis will be conducted during Phase II. ORR will be evaluated for the first 9 patients in each Phase II cohort to determine whether enrollment may continue (see Section 4.1).

12 Changes in the Planned Analysis

There were no substantial changes from the planned analyses described in the protocol version 4.0, dated 24 Feb 2020 to those presented in this SAP. The following minor detail has changed from the protocol:

- All Patients Set has been added to allow for additional disposition summaries to be conducted
- Safety RP2D Analysis Set has been added to allow for some analyses to be conducted on patients pooled across phases if they receive RP2D.

13 References

14 Appendices

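### The SAP plans no analysis of ADA impact on PK or of dose proportionality, makes half-life and clearance optional, and declares none of these departures from the protocol

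*SAP*

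**What the plan says.** **ADA.** Protocol Table 4-1 gives the secondary endpoint as "Incidence of anti- IMCnyeso antibody formation and its impact on PK". The Amendment 2 log in protocol 13.5.2 shows that the PK part was deliberate: "The secondary ADA endpoint was updated to include the impact of ADA on PK". SAP 3.2.2 shortens the endpoint to "The incidence of anti-IMCnyeso antibody formation". SAP 10.2 states "The frequency of ADA at baseline and following treatment will be summarized" and goes on to titer, onset and duration.

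**Dose proportionality.** Protocol 9.6.3 says that log-transformed AUC and Cmax estimates "will be examined using the Power Model", with the slope b and its confidence interval set against the value 1. SAP 10.1 contains no such model.

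**PK parameters.** Protocol Table 9-1 lists AUClast, AUCinf, Cmax, Tmax, t1/2, CL, Vz and the accumulation ratio as parameters to be analyzed. SAP 10.1 fixes Tmax, Cmax and either AUClast (C1D1) or AUCtau (C1D8, C1D15). For the rest it says "Additional PK parameters may be calculated as the analysts determines meaningful at the time of the analysis", with CL, t1/2 and Vss as examples. SAP 3.2.2 nevertheless names t1/2 among the PK parameters to be analyzed in both phases.

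**Declaration.** SAP 12 states "There were no substantial changes from the planned analyses described in the protocol version 4.0" and lists two minor changes, both added analysis sets.

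**The concern.** A SAP may refine or drop a protocol analysis, but it should say so. Here the stated endpoint loses half its content, a model the protocol commits to disappears, and a parameter that SAP 3.2.2 names becomes discretionary in SAP 10.1. A reader who relies on SAP 12 would believe that the PK and ADA plan is unchanged.

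The two missing analyses bear on interpretation. Weekly dosing continues until treatment is discontinued, so whether ADA lowers exposure matters for reading later-cycle data. The starting-dose rationale in protocol 6.9 ties toxicity to peak concentration and cites linear kinetics from mice. The power model was the protocol's one firmly planned check of proportionality in patients, and SAP Table 1 now runs from 3 to 300 mcg, a 100-fold range.

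**Working it through.** The plan gives no figure to reproduce. The check is a comparison of texts, followed by a test of whether the missing analyses are feasible.

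**1. Side by side**

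| Item | Protocol | SAP |
|---|---|---|
| ADA impact on PK | Secondary endpoint (Table 4-1); no method in 9.6.3 | Absent from 3.2.2, 10.1 and 10.2 |
| Power model, slope b with CI | Firm (9.6.3) | Absent from 10.1 |
| t1/2, CL | Table 9-1 | Optional (10.1); t1/2 still named in 3.2.2 |
| AUCinf, Vz, accumulation ratio | Table 9-1 | Not named in 10.1 |
| Declared in SAP 12 | – | None of these |

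The only use of a PK value in SAP 10.2 is the assay drug-tolerance check on negative samples (200 ng/mL). That is not an effect of ADA on exposure. No visible title in SAP 14.2 supplies either missing analysis. This is supporting evidence only: one parameter table (14.3.9.1) has a redacted word in its title, and the list omits some plots that SAP 10.1 commits to.

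**2. Are the data there?** Protocol Table 7-2 puts ADA samples on the same days as pre-dose and end-of-infusion (EOI) PK samples: C1D1, C1D8, C1D15, C2D1, C3D1 and Day 1 of later odd cycles. Full PK profiles fall on C1D1 and C1D8 for fixed dosing, and on C1D8 and C1D15 for intra-patient escalation (IPE; Table 13-13).

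**3. Is the slope estimable?** SAP Table 1 gives 4+3+5+3+5+4+6 = 30 Phase I patients, the last 6 planned. For log(parameter) = a + b·log(dose) with one observation per patient, the 95% half-width for b is t(0.975, n−2)·s/√Sxx, with s = √ln(1+CV²). The documents give no CV, so 30%, 50% and 80% are assumed.

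- Fixed-dose patients (3, 10, 30, 100 mcg; n = 4, 3, 5, 3): Sxx = 23.9 and t = 2.160 on 13 df. At 30% CV, s = 0.294, so 2.160 × 0.294/4.889 = 0.13. At 50% and 80% the half-width is 0.21 and 0.31.
- All 30 C1D1 doses (cohorts 5–7 start at 30 mcg): 0.12, 0.19 and 0.28.

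Both sets cover only 3 to 100 mcg. The 180 and 300 mcg doses are given later in Cycle 1 to IPE patients, so using them needs repeated doses per patient and a patient-specific intercept. Protocol 9.6.3 already describes the intercept as depending on the patient.

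**4. Is half-life derivable at the lowest dose?** Protocol 6.9 assumes a volume of 8 L: 3 mcg/8 L = 375 pg/mL. The assay limit in SAP 10.1 is 25 pg/mL, and log2(375/25) = 3.9 half-lives. At the 2–3 h mouse half-life in protocol 6.9 that is about 8–12 h, within the fixed-dose C1D1 sampling window. A 1–2 h infusion lowers the peak somewhat, so this is slightly generous.

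**5. What must a restored Cmax model control?** Protocol 6.4 allows infusion time to fall from 2 h to 1 h at C1D8 and to 30 min at C3D1. In a one-compartment model Cmax is proportional to (1−e^(−kT))/(kT), with k = ln2/half-life.

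- Half-life 2 h: 0.845 (T = 1 h) over 0.721 (T = 2 h) = 1.17.
- Half-life 3 h: 0.893 over 0.801 = 1.12 (1.115 before rounding).

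Halving the duration thus raises Cmax by about 12–17%. Over a 30-to-100 mcg step within a patient, b shifts by ln(1.115)/ln(3.33) = 0.09 to ln(1.17)/ln(3.33) = 0.13. That is close to the half-width at 30% CV, so duration cannot be ignored.

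**The case against.** The best defense is that little specified work was lost. Protocol 9.6.3 itself plans only ADA frequency and gives no ADA-PK method, and SAP 10.2 repeats that commitment. The power model is not an endpoint in Table 4-1, and the protocol calls it preliminary. Half-life sits in a list of examples in both endpoint sections. The SAP tests no formal hypothesis. All of this is true and limits the weight of the point. It does not explain why the endpoint wording was cut, why a committed model is gone, or why SAP 12 is silent.

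A reader might infer several stronger things that the documents do not support:

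- *That the questions cannot be answered, or that ADA-related loss of exposure would be missed.* SAP 10.1 keeps individual profiles, a plot of pre-dose and EOI concentrations by cycle, and parameters by cohort and dose. SAP 10.2 gives each patient's ADA status and onset. Both sections allow a stand-alone report, and the protocol leaves population PK open. Falling exposure could be seen, though not summarized by ADA status.
- *That SAP 12 denies any change.* It denies substantial change and lists two minor ones.
- *That optional half-life undermines the 28-day DLT period or the 8-hour monitoring option.* Those rest on acute onset and observed cytokine release timing. The documents cite half-life only for the 30-day follow-up and the one-night hospitalization, as an existing class figure below 24 hours.
- *That discretion over half-life signals selective reporting.* Nothing shows a direction in which the choice would favor the drug.

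**Conclusion.** The point stands as a gap between protocol and SAP that should be reconciled. The PK half of the secondary ADA endpoint and the protocol's power model have no planned analysis. Two Table 9-1 parameters (t1/2, CL) are discretionary and three (AUCinf, Vz, accumulation ratio) are not named. SAP 3.2.2 and 10.1 disagree on t1/2, and SAP 12 declares none of it.

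This rests on the text of the two documents and on no assumed figure. The feasibility results (slope half-width 0.13 to 0.31 from fixed-dose patients; half-life observable at 3 mcg) do rest on assumed CVs, the protocol's 8 L volume and a mouse half-life. They show only that the analyses are practicable. No primary endpoint, dose-escalation rule or Phase II continuation rule changes.

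**What to change.** 1. **SAP 3.2.2 and 10.2.** Restore the PK part of the ADA endpoint. Add a descriptive comparison of EOI concentration by ADA status within the same dose level and infusion duration, and individual concentration-over-time plots that mark the first positive ADA result. Pooling across doses by dose normalization would assume b = 1, so compare within dose. Give within-patient before/after ratios only where visits with the same dose and infusion duration exist. If infusions are shortened as permitted, the matching ADA visits before C3D1 are at most C1D8, C1D15 and C2D1.
2. **SAP 10.1, dose proportionality.** Restore the protocol's power model for Cmax and AUC, with b, its 95% CI and a patient-specific intercept. For Cmax, restrict to one infusion duration or adjust for it. Take AUC only from full-sampling days: C1D1 and C1D8 for fixed dosing, C1D8 and C1D15 for IPE. IPE C1D1 has only pre-dose, EOI, 8 h and 24 h samples.
3. **SAP 10.1, parameters.** Make t1/2 and the other Table 9-1 parameters fixed outputs on full-sampling days, with a stated rule for when each is derivable.
4. **SAP 12.** List any item dropped on purpose, with the reason.

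Cost: SAP wording and two or three outputs. No new samples or patients are needed.
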